5.1.3 Subject Exclusion Criteria

The subject must be excluded from participating in the trial if the subject:

1. Subject is under the age of legal consent.
2. Female subject is pregnant, or has intended to become pregnant during the study, or is nursing.
3. Subject is mentally or legally incapacitated, has significant emotional problems at the time of pre-study (screening) visit or expected during the conduct of the study or has a history of a clinically significant psychiatric disorder over the last 5 years. Subjects who have had situational depression may be enrolled in the study at the discretion of the investigator.
4. Subject has received systemic antifungal therapy (oral, intravenous, or inhaled) within 30 days of study enrollment for reasons other than antifungal prophylaxis.
5. A subject has known (including a possible, probable, or proven fungal infection per EORTC/MSG version 2008 criteria) [8] or suspected invasive or systemic fungal infection at Baseline.
6. Subject has taken posaconazole within 10 days prior to study enrollment.

7. Subject has had major surgery, donated or lost 1 unit of blood (approximately 500 mL) or participated in another investigational study within 4 weeks prior to the pre-study (screening). The 4 week window will be derived from the date of the last study procedure (i.e. post-study, AE follow-up, etc.) in the previous study to the pre-study/screening visit of the current study.
8. Subject has had a history of Type I hypersensitivity or idiosyncratic reactions to azole agents.
9. Subject has a history of significant multiple and/or severe allergies (including latex allergy), or has had an anaphylactic reaction or significant intolerance to prescription or non-prescription drugs or food.
10. Subject has had moderate or severe liver dysfunction at baseline, in this protocol defined as aspartate aminotransferase (AST) or alanine aminotransferase (ALT) levels greater than three times the upper limit of normal (ULN), AND a total bilirubin level greater than two times the ULN.
11. Subject with chronic active hepatitis, cirrhosis, Hepatocellular Carcinoma (HCC), or other hepatic disease caused by virus.
12. Subject has had an ECG with a prolonged QTc interval by manual reading: QTc greater than 500 msec.
13. Excluded treatments prior to specific study phases. Subject has taken one of the following drugs listed in the [Table 1](#) below more recently than the indicated washout period prior to study treatment.
14. Excluded treatments during the study treatment period. Subject has to take one of the following drugs that are listed in [Table 1](#) during the study.

Table 1 Prohibited Medications Prior to Start of Study Treatment and During Study Treatment

Prohibited Medications Prior to Start of Study Treatment and During Study Treatment	Washout Period ^a
Systemic antifungal therapy (oral, intravenous or inhaled) other than study drugs for reasons other than antifungal prophylaxis.	30 days
Investigational drugs (new chemical or biological entities): Investigational use of approved products or chemotherapy regimens may be permitted with the approval of the sponsor's project physician prior to use.	30 days
Prophylaxis of IFI with posaconazole.	10 days
Medications that are known to interact with azoles and may lead to life-threatening side effects: astemizole, cisapride, ebastine, halofantrine, pimozide, quinidine, and terfenadine.	10 days (astemizole) 24 hours (others)
Ergot alkaloids (ergotamine, dihydroergotamine or other licensed or investigational members of this class).	2 days
Medications known to lower the serum concentration/efficacy of azole antifungals: barbiturates, carbamazepine, cimetidine, isoniazid, phenytoin, rifabutin, rifampin, and St. John's Wort (hypericum perforatum).	24 hours
Prophylactic use of nonabsorbable antifungal drugs: Nasal sprays of amphotericin B and aerosolized amphotericin B are prohibited.	24 hours
HMG-CoA reductase inhibitors metabolized via CYP3A4 (eg, simvastatin, lovastatin, and atorvastatin).	24 hours
Cyclophosphamide ^b	24 hours

a: These waiting times should be observed prior to start of study treatment and during study treatment in subjects receiving a prohibited drug. No concurrent use is permitted. Deviations from these washout periods must be approved by the sponsor prior to use of study drug or prohibited agent.

b: Low dose cyclophosphamide use is allowed during the treatment period with a temporary interruption of study therapy on the day of cyclophosphamide dosing.

HMG-CoA=beta-hydroxy-beta-methylglutaryl-CoA; IFI = invasive fungal infection

15. There is any concern by the investigator regarding the safe participation of the subject in the study, or for any other reason, the investigator considers the subject inappropriate for participation in the study. Subject has had any condition that, in the opinion of the investigator, may interfere with optimal participation in the study, i.e., any condition requiring the use of prohibited drugs or unstable medical conditions other than the hematological disorder such as cardiac or neurologic disorder or impairment expected to be unstable or progressive during the course of this study (e.g., seizures or demyelinating syndromes, acute myocardial infarction within 3 months of study entry, myocardial ischemia, or unstable congestive heart failure, unstable arrhythmias, atrial fibrillation with ventricular rate <60/min, or history of torsades de pointes, symptomatic ventricular or sustained arrhythmias, unstable electrolyte abnormalities [e.g., \geq Grade 2 hypokalaemia or hypomagnesaemia]).
16. Subject has had prior enrollment in this study, or other POS studies within 90 days of study entry.
17. Subject has had an Eastern Cooperative Oncology Group (ECOG) [9] performance status >2 prior to induction chemotherapy for the subject's underlying disease.

18. Subject has had a creatinine clearance level (measured or calculated) below 50 mL/min based on the Cockcroft-Gault equation; the Cockcroft-Gault equation is as follows:

$$\text{ClCr} = (140 - \text{age[yr]})(\text{body wt [kg]}) * (0.85 \text{ if female}) \\ (72)(\text{serum creatinine [mg/dL]})$$

When creatinine is measured in micromole/litre, use the following formula:

$$\text{ClCr} = (140 - \text{age[yr]})(\text{body wt[kg]}) * (0.85 \text{ if female}) \\ (72)(\text{serum creatinine [micromol/L]} \times 0.0113)$$

19. Subject has known or suspected Gilbert's disease.

20. Subject is or has an immediate family member (e.g., spouse, parent/legal guardian, sibling or child) who is investigational site or sponsor staff directly involved with this trial.

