 - a. Standard intensive induction chemotherapy, anthracycline-based or other accepted regimen (excluding any investigational agent), for a new diagnosis of acute myelogenous leukemia (AML);
 - b. Reinduction chemotherapy for AML in first relapse; or
 - c. Myelosuppressive induction therapy for myelodysplastic syndromes (MDS) in transformation to AML or other diagnoses of secondary AML (therapy related, antecedent hematological disorders) other than chronic myelogenous leukemia in blast crisis
5. Each subject must be free of any clinically significant disease (other than the primary hematologic disease) that would interfere with the administration of study medication or study evaluations.
6. Each subject must be able to tolerate the administration of central IV solution medication.
7. Subject is willing to comply with the study restrictions.
8. Each subject must be willing and able to provide written informed consent for the trial. The legal representative for a subject who otherwise is unable to provide independent consent at the discretion of the investigator may provide written informed consent for the subject. The subject may also provide consent for Future Biomedical Research. However, the subject may participate in the main trial without participating in Future Biomedical Research.

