5.8 Subject Withdrawal/Discontinuation Criteria

Subjects may withdraw consent at any time for any reason or be dropped from the trial at the discretion of the investigator should any untoward effect occur. In addition, a subject may be withdrawn by the investigator or the Sponsor if enrollment into the trial is inappropriate, the trial plan is violated, or for administrative and/or other safety reasons. Specific details regarding discontinuation or withdrawal procedures; including specific details regarding withdrawal from Future Biomedical Research, are provided in Section 7.1.4 – Other Procedures.

Discontinuation from treatment is “permanent”. Once a subject is discontinued, he/she shall not be allowed to restart treatment.

A subject must be discontinued from the trial for any of the following reasons:

- The subject or legal representative (such as a parent or legal guardian) withdraws consent.
- Documentation of a fungal infection (proven, probable or possible IFI) according to the European Organization for Research and Treatment of Cancer/Invasive Fungal Infections and the National Institute of Allergy and Infectious Diseases Mycoses Study Group (EORTC-MSG version 2008) criteria [8];
- Subjects with a prolonged QTc interval on a manual measurement (QTc greater than 500 msec);
- A subject who, prior to start of study treatment and during study treatment, requires any of the prohibited medications listed in [Table 1](#) of Section 5.1.3.

- Inability to continue to take study medication according to schedule (See Section 5.2.2);
- Failure to comply with the dosing, evaluations, or other requirements of the study;
- A subject with liver function tests (ALT, AST, or total bilirubin) greater than 10 x ULN or other clinical or histopathologic evidence of drug-induced hepatotoxicity;
- A subject who has recovered from neutropenia ($ANC \geq 500/\text{mm}^3$) and has not considered risk factors of IFI remain at the discretion of investigator;
- The subject interrupts trial medication administration for more than 3 consecutive days;
- The subject has a medical condition or personal circumstance which, in the opinion of the investigator and/or Sponsor, places the subject at unnecessary risk through continued participation in the trial or does not allow the subject to adhere to the requirements of the protocol;
- The subject has a confirmed positive serum pregnancy test.

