7.2.3.2 Events of Clinical Interest

Selected non-serious and serious adverse events are also known as Events of Clinical Interest (ECI) and must be reported to the Sponsor.

For the time period beginning when the consent form is signed until treatment allocation/randomization, any ECI, or follow up to an ECI, that occurs to any subject must be

reported within 24 hours to the Sponsor if it causes the subject to be excluded from the trial, or is the result of a protocol-specified intervention, including but not limited to washout or discontinuation of usual therapy, diet, placebo treatment or a procedure.

For the time period beginning at treatment allocation/randomization through 30 days following cessation of treatment, any ECI, or follow up to an ECI, whether or not related to the Sponsor's product, must be reported within 24 hours to the Sponsor, either by electronic media or paper. Electronic reporting procedures can be found in the EDC data entry guidelines. Paper reporting procedures can be found in the Investigator Trial File Binder (or equivalent).

Events of clinical interest for this trial include:

1. an overdose of Sponsor's product, as defined in Section 7.2.1 - Definition of an Overdose for This Protocol and Reporting of Overdose to the Sponsor, that is not associated with clinical symptoms or abnormal laboratory results.
2. an elevated AST or ALT lab value that is greater than or equal to 3X the upper limit of normal and an elevated total bilirubin lab value that is greater than or equal to 2X the upper limit of normal and, at the same time, an alkaline phosphatase lab value that is less than 2X the upper limit of normal, as determined by way of protocol-specified laboratory testing or unscheduled laboratory testing.*

***Note:** These criteria are based upon available regulatory guidance documents. The purpose of the criteria is to specify a threshold of abnormal hepatic tests that must trigger an additional evaluation for an underlying etiology. The trial site guidance for assessment and follow up of these criteria can be found in the Investigator Trial File Binder (or equivalent).

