It may also be appropriate to conduct additional evaluation for an underlying etiology in the setting of abnormalities of liver blood tests including AST, ALT, bilirubin, and alkaline phosphatase that do not meet the criteria noted above. In these cases, the decision to proceed with additional evaluation will be made through consultation between the study investigators and the Sponsor Clinical Director. However, abnormalities of liver blood tests that do not meet the criteria noted above are not ECIs for this trial.

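### The numeric entry rules can admit a subject with one liver test already above the 10 x ULN limit at which section 5.8 requires permanent discontinuation

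*Combined protocol and SAP*

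**What the plan says.** **Entry.** Section 5.1.3, criterion 10, defines moderate or severe liver dysfunction at baseline as AST or ALT above 3 x ULN "AND a total bilirubin level greater than two times the ULN". Both parts must be met. No other entry criterion sets a numeric limit for transaminases or bilirubin. Criteria 11 (chronic active hepatitis, cirrhosis, hepatocellular carcinoma, viral liver disease) and 19 (Gilbert's disease) are diagnoses.

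**Stopping.** Section 5.8 lists among its mandatory reasons for discontinuation: "A subject with liver function tests (ALT, AST, or total bilirubin) greater than 10 x ULN". Any one test is enough. The same item continues: "greater than 10 x ULN or other clinical or histopathologic evidence of drug-induced hepatotoxicity". Discontinuation is final: "Once a subject is discontinued, he/she shall not be allowed to restart treatment".

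**Events of clinical interest.** The hepatic rule in section 7.2.3.2 is also joint. It needs AST or ALT at or above 3 x ULN, "and an elevated total bilirubin lab value that is greater than or equal to 2X the upper limit of normal", with alkaline phosphatase below 2 x ULN. The section adds that "abnormalities of liver blood tests that do not meet the criteria noted above are not ECIs for this trial", although it allows further evaluation of such abnormalities in consultation with the Sponsor Clinical Director.

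**Judgement at entry.** Inclusion 5 says "Each subject must be free of any clinically significant disease (other than the primary hematologic disease" that would interfere with study medication or evaluations. Exclusion 15 opens with "There is any concern by the investigator regarding the safe participation of the subject in the study". Appendix 12.5, clause D, makes exclusion mandatory once the significance of an abnormal value is clinically uncertain.

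**The concern.** Entry and stopping rules for the same laboratory tests should fit together: nobody should qualify on a value that would require immediate and permanent withdrawal. Here the entry rule looks at a combination and the stopping rule looks at each test alone, so they can disagree. Among the numeric entry, stopping and ECI rules, only section 5.8 acts on one liver test, and it acts after enrolment.

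Two things are at stake. One is protection of a small number of subjects with a large isolated rise, in a population that is receiving or about to receive induction chemotherapy. The other is consistent handling across sites: the protocol does not say whether such a subject should be kept out, enrolled and then withdrawn, or enrolled and treated.

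**Working it through.** No sample size, power or error rate is involved. The check runs liver-test profiles through the stated rules.

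**Rules, in multiples of ULN**

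- Exclusion 10 (5.1.3): (AST > 3 or ALT > 3) and bilirubin > 2.
- Stopping limit (5.8): AST > 10 or ALT > 10 or bilirubin > 10.
- Proposed exclusion 10: the current rule, or any one of the three tests > 10.

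**Results**

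| AST / ALT / bilirubin | Excluded by criterion 10 | Past the 5.8 limit | Excluded by proposed rule |
|---|---|---|---|
| 1 / 11 / 1 | no | yes | yes |
| 11 / 1 / 1 | no | yes | yes |
| 1 / 1 / 11 | no | yes | yes |
| 11 / 11 / 2 | no | yes | yes |
| 3 / 3 / 11 | no | yes | yes |
| 11 / 11 / 2.1 | yes | yes | yes |
| 4 / 1 / 2.1 | yes | no | yes |
| 10 / 10 / 2 | no | no | no |

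The first five rows are the gap: admitted by the numeric rules, yet past the stopping limit. Rows four and six differ only in bilirubin, 2 against 2.1 x ULN.

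The two examples in the summary behave the same way. With the higher transaminase at 11 and bilirubin at 1.5, criterion 10 fails on bilirubin (1.5 is not above 2), while 5.8 is met (11 > 10). With bilirubin at 11 and the higher transaminase at 2.5, criterion 10 fails on the transaminase (2.5 is not above 3), while 5.8 is met. Neither is an ECI, because in each case one half of the joint condition is unmet (1.5 < 2; 2.5 < 3).

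**Does another rule close the gap numerically?** No. Appendix 12.5, clause B, only refers back to the inclusion and exclusion parameters, which these subjects do not breach.

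**Timing, a narrower point.** The flow chart schedules chemistry at screening (Day -14 to Day -2) and on Day 1, with a second inclusion/exclusion review at Day -1. Section 7.1.5.2 lists what confirms eligibility at Day -1 or pre-dose: pregnancy test, ECG, vital signs, concomitant medication and adverse events. Liver tests are not on that list. Flow-chart footnote p requires the Day 1 laboratory samples to be drawn before treatment, but requires a result before treatment only for beta-hCG. A value above 10 x ULN at screening would therefore be seen before dosing. A rise after screening could be missed until the Day 1 result returns.

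**Comparison within the protocol.** For QTc, the entry limit (5.1.3, criterion 12) and the stopping limit (5.8) are the same: above 500 msec on manual reading.

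**The case against.** The strongest reply is that these subjects would not be enrolled in practice. An investigator would need to have no safety concern under exclusion 15, and no clinical uncertainty under Appendix 12.5 D, about a value that the same protocol treats as a mandatory stop. Exclusions 11 and 19 remove some causes of isolated rises. Section 5.8 also allows withdrawal where enrolment is inappropriate. This largely stands, and it is why the expected frequency is low. It does not remove the inconsistency. These are judgements or diagnoses, and inclusion 5 sets aside the primary hematologic disease, to which a liver abnormality might be attributed.

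A second reply is that 5.8 closes the gap itself. It states no baseline exemption, and its prohibited-medication item expressly reaches back before the start of treatment. On that reading a known pre-dose ALT of 11 x ULN leads straight to discontinuation. That also stands, but it means enrolling a subject who must then be withdrawn.

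The opposite reading is that 5.8 concerns on-treatment changes only, which its reference to drug-induced hepatotoxicity could suggest. A reader might then infer that the subject is left without any liver stopping limit. The documents do not support that. Only the test already raised loses its limit. With ALT at 11 x ULN, bilirubin above 10 x ULN still applies, as does AST if it started below 10 x ULN, and so does the clause on other evidence of hepatotoxicity. That subject also already meets the transaminase half of the ECI rule, so bilirubin reaching 2 x ULN with alkaline phosphatase below 2 x ULN would trigger a report within 24 hours.

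Finally, matching limits for QTc do not prove that liver limits must match. The QTc rule is a useful precedent, no more.

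**Conclusion.** The mismatch is real on the text: the numeric entry rules admit subjects whom 5.8, read as written, requires to be discontinued permanently. Severity is minor.

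The conclusion rests on reading criterion 10 as it is written, with both parts required, and on the absence of any other numeric transaminase or bilirubin limit at entry. How often it would matter cannot be estimated, because the documents give no baseline liver-test distribution; that it is probably low is a judgement based on the other safeguards.

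It would go too far to infer that such subjects are unprotected, or that they would go unnoticed until the next scheduled chemistry at Day 10 (±1). The Day 1 sample must be drawn before dosing and its result documented, and if 5.8 has no baseline exemption it acts when that result returns. Section 7.1 also allows unscheduled tests. The pharmacokinetic objective is not threatened.

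**What to change.** 1. In section 5.1.3, keep the joint 3 x / 2 x definition in criterion 10 and add: *or ALT, AST or total bilirubin >10 x ULN on the most recent pre-dose test*.
2. In section 7.1.5.2, add review of a liver result before the first dose to the items that confirm eligibility. This can be a screening result from within 72 hours before dosing, or the Day 1 pre-dose sample.

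Changing the AND in criterion 10 to OR would also close the gap, but it would exclude moderate isolated rises such as ALT 6 x ULN with bilirubin 1.5 x ULN. The proposed clause leaves these eligible.

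The cost is one clause and one checklist item. No extra blood draw is needed: footnote p already accepts screening results from within 72 hours as Day 1 results, and section 7.1.3.1 lets pre-dose laboratory tests be done up to 24 hours before dosing. The downside is a rare extra screen failure or a short delay to the first infusion while a result is awaited.

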5.2.2 Timing of Dose Administration

MK-5592 IV solution will be administrated through central line for approximately 90 minutes, the residual volume, if any, should be documented. Subjects will have their IV infusions began at approximately the same time each day. The first three IV infusions must be given not less than 10 hours or no more than 14 hours apart. The subsequent IV infusions must be given not less than 22 hours or no more than 26 hours apart, in order to control one source of variability in drug levels. MK-5592 IV solution will be dosing without regard to food intake.

If the dosing of MK-5592 IV solution for the other days besides the day 1 is delayed, the dose of MK-5592 IV solution for the remaining days of the study should be taken following completion of the trough PK blood sampling (see flow chart for applicable study days) with at least 8 hours separating the prior day's dosing. Every attempt should be made to ensure that the subject given study medication once daily following the Q12h dosing on Day 1.

If the treatment of the subject switches to POS oral suspension at the discretion of investigator from Day 11 (± 1) to Day 28 or EOT, which occurs first. For subjects in subgroup 1, the intensive PK for POS IV solution must be obtained before switching to oral suspension. The oral suspension should be given under the guidance of physicians per local label. The POS oral suspension should be administered with food or immediately after eating (i.e., within 20 minutes). The investigator may switch the subject back to POS IV solution if the subject is unable to dose with food or tolerate oral medication. Subjects who vomit within 30 minutes of POS oral administration should be given a single replacement dose as soon as possible or per guidance of the physician, following appropriate antiemetic treatment.

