*Change from Grade 0 to 2 at baseline to Grade 3 or 4 during the study. These data are presented in the form X/Y, where X represents the number of patients who met the criterion as indicated, and Y represents the number of patients who had a baseline observation and at least one post-baseline observation.

CTC = Common Toxicity Criteria; AST= Aspartate Aminotransferase; ALT= Alanine Aminotransferase.

The number of patients treated for OPC with clinically significant liver function test (LFT) abnormalities at any time during the studies is provided in Table 5. (LFT abnormalities were present in some of these patients prior to initiation of the study drug).

TABLE 5: Clinically Significant Laboratory Test Abnormalities without Regard to Baseline Value

Laboratory Test	Controlled		Refractory
	Posaconazole	Fluconazole	Posaconazole
	n=557(%)	n=262(%)	n=239(%)
ALT > 3.0 x ULN	16/537 (3)	13/254 (5)	25/226 (11)
AST > 3.0 x ULN	33/537 (6)	26/254 (10)	39/223 (17)
Total Bilirubin > 1.5 x ULN	15/536 (3)	5/254 (2)	9/197 (5)
Alkaline Phosphatase > 3.0 x ULN	17/535 (3)	15/253 (6)	24/190 (13)

ALT= Alanine Aminotransferase; AST= Aspartate Aminotransferase.

3. Postmarketing Experience

No clinically significant postmarketing adverse reactions were identified that have not previously been reported during clinical trials experience.

[Contraindications]

1. Hypersensitivity

NOXAFIL is contraindicated in persons with known hypersensitivity to posaconazole, any component of NOXAFIL, or other azole antifungal agents.

2. Use with Sirolimus

NOXAFIL is contraindicated with sirolimus. Concomitant administration of NOXAFIL with sirolimus increases the sirolimus blood concentrations by approximately 9 fold and can result in sirolimus toxicity.

3. QT Prolongation with Concomitant Use with CYP3A4 Substrates

NOXAFIL is contraindicated with CYP3A4 substrates that prolong the QT interval. Concomitant administration of NOXAFIL with the CYP3A4 substrates, terfenadine, astemizole, cisapride, pimozide and quinidine may result in increased plasma concentrations of these drugs, leading to QTc prolongation and rare occurrences of torsades de pointes.

4. HMG-CoA Reductase Inhibitors Primarily Metabolized Through CYP3A4

Coadministration with the HMG-CoA reductase inhibitors that are primarily metabolized through CYP3A4 (e.g., atorvastatin, lovastatin, and simvastatin) is contraindicated since increased plasma concentration of these drugs can lead to rhabdomyolysis.

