Of the 605 patients randomized to posaconazole in the prophylaxis clinical trials, 63 (10%) were ≥ 65 years of age. In addition, 48 patients treated with ≥ 800 -mg/day posaconazole in another indication were ≥ 65 years of age. No overall differences in safety were observed between the geriatric patients and younger patients; therefore, no dosage adjustment is recommended for geriatric patients.

The pharmacokinetics of posaconazole are comparable in young and elderly subjects (≥ 65 years of age). No adjustment in the dosage of NOXAFIL is necessary in elderly patients (≥ 65 years of age) based on age.

No overall differences in the pharmacokinetics and safety were observed between elderly and young subjects during clinical trials, but greater sensitivity of some older individuals cannot be ruled out.

[Drug Interactions]

Posaconazole is primarily metabolized via UDP glucuronidation and is a substrate of p-glycoprotein efflux. Therefore, inhibitors or inducers of these clearance pathways may affect posaconazole plasma concentrations. Posaconazole is also a strong inhibitor of CYP3A4. Therefore, plasma concentrations of drugs predominantly metabolized by CYP3A4 may be increased by posaconazole.

1. Immunosuppressants Metabolized by CYP3A4

Sirolimus: Repeat dose administration of oral posaconazole (400 mg oral suspension twice daily for 16 days) increased the Cmax and AUC of sirolimus (2 mg single dose) an average of 6.7-fold and 8.9-fold, respectively, in healthy subjects. When initiating therapy in patients already taking sirolimus, the dose of sirolimus should be reduced (e.g., to about 1/10 of the current dose) with frequent monitoring of sirolimus whole blood trough concentrations. Sirolimus concentrations should be performed upon initiation, during coadministration, and at discontinuation of posaconazole treatment, with sirolimus doses adjusted accordingly.

Tacrolimus: Posaconazole has been shown to significantly increase the Cmax and AUC of tacrolimus (0.05 mg/kg single dose) by 121% and 358%, respectively. At initiation of posaconazole treatment, reduce the tacrolimus dose to approximately one-third of the original dose. Frequent monitoring of tacrolimus whole blood trough concentrations should be performed during and at discontinuation of posaconazole treatment and the tacrolimus dose adjusted accordingly.

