Cyclosporine: Posaconazole 200mg oral suspension once daily has been shown to increase cyclosporine whole blood concentrations in heart transplant patients upon initiation of posaconazole treatment. It is recommended to reduce cyclosporine dose to approximately three-fourths of the original dose upon initiation of posaconazole treatment. Frequent monitoring of cyclosporine whole blood trough concentrations should be performed during and at discontinuation of posaconazole treatment and the cyclosporine dose adjusted accordingly.

2. CYP3A4 Substrates

Concomitant administration of posaconazole with CYP3A4 substrates such as pimozide and quinidine may result in increased plasma concentrations of these drugs, leading to QTc prolongation and rare occurrences of torsades de pointes. Therefore, posaconazole is contraindicated with these drugs.

3. HMG-CoA Reductase Inhibitors (Statins) Primarily Metabolized Through CYP3A4

Repeat dose administration of oral posaconazole (50, 100, and 200 mg oral suspension once daily for 13 days) increased the Cmax and AUC of simvastatin (40 mg single dose) an average of 7.4- to 11.4-fold, and 5.7- to 10.6-fold, respectively. Increased HMG-CoA reductase inhibitor concentrations in plasma can be associated with rhabdomyolysis. Coadministration of posaconazole and HMG-CoA reductase inhibitors primarily metabolized through CYP3A4 is contraindicated.

4. Ergot Alkaloids

Most of the ergot alkaloids are substrates of CYP3A4. Posaconazole may increase the plasma concentrations of ergot alkaloids (ergotamine and dihydroergotamine) which may lead to ergotism. Therefore, posaconazole is contraindicated with ergot alkaloids.

5. Benzodiazepines Metabolized by CYP3A4

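### Table 1 bans every drug named in the appended oral-suspension label's interaction contraindications except sirolimus, which is left under a general CYP3A4 caution

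*Combined protocol and SAP*

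**What the plan says.** Exclusion 13 (use before treatment), exclusion 14 (need during treatment) and the prohibited-medication rule in section 5.8 all take their content from Table 1 in section 5.1.3. The row closest to this point lists "Medications that are known to interact with azoles and may lead to life-threatening side effects: astemizole, cisapride, ebastine, halofantrine, pimozide, quinidine, and terfenadine". Other rows ban ergot alkaloids and the statins metabolised by CYP3A4. Sirolimus is in no row, and the protocol body does not name it.

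For CYP3A4 substrates outside Table 1, section 7.1.1.5.2 warns that exposure may rise greatly. It asks for caution, close monitoring of concentrations or adverse events, and dose adjustment. It does not ban them.

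The circular for the oral suspension (appendix 12.10) states under Contraindications that "NOXAFIL is contraindicated with sirolimus" and gives the reason: "Concomitant administration of NOXAFIL with sirolimus increases the sirolimus blood concentrations by approximately 9 fold and can result in sirolimus toxicity". Under Drug Interactions the same circular says that, when therapy starts in a patient already taking it, "the dose of sirolimus should be reduced (e.g., to about 1/10 of the current dose"), with frequent trough monitoring.

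The suspension is a study drug from Day 11 (±1), at the investigator's discretion. Section 5.2.2 says: "The oral suspension should be given under the guidance of physicians per local label".

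**The concern.** Table 1 is the working control: a site checking eligibility or continued treatment looks there. A drug that is absent from it defaults to the general caution in 7.1.1.5.2. For sirolimus, that default allows a combination that the label of one of the two study formulations contraindicates.

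The label itself separates sirolimus from related drugs. Cyclosporine and tacrolimus appear under Precautions, with monitoring and dose adjustment; sirolimus appears under Contraindications. The general caution in 7.1.1.5.2 removes that distinction. Section 7.1.5.5 does not allow the study drug dose to be modified, so a site could manage the interaction only by changing sirolimus or stopping the study drug.

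At stake is drug toxicity in a severely immunocompromised subject who is enrolled or kept on sirolimus and then switched to the suspension. A site that does consult the label finds two different instructions, and the protocol does not say which one governs.

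**Working it through.** No sample size or power figure is involved. The check is a comparison of lists.

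**Step 1. Named drugs in the circular's interaction contraindications, set against Table 1.** Contraindication 1 is hypersensitivity and is left out.

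| Group (circular, Contraindications 2 to 5) | Drugs named | In Table 1 |
|---|---|---|
| Sirolimus | 1 | 0 |
| QT-prolonging CYP3A4 substrates: terfenadine, astemizole, cisapride, pimozide, quinidine | 5 | 5 |
| CYP3A4 statins: atorvastatin, lovastatin, simvastatin | 3 | 3 |
| Ergot alkaloids: ergotamine, dihydroergotamine | 2 | 2 |
| Total | 1 + 5 + 3 + 2 = 11 | 0 + 5 + 3 + 2 = 10 |

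By drug, 10 of 11 are banned; by group, 3 of 4.

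**Step 2. Is the circular consistent with itself?** Its Drug Interactions section returns to all four groups.

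- QT drugs: "Therefore, posaconazole is contraindicated with these drugs".
- Statins: "Coadministration of posaconazole and HMG-CoA reductase inhibitors primarily metabolized through CYP3A4 is contraindicated".
- Ergot alkaloids: "Therefore, posaconazole is contraindicated with ergot alkaloids".
- Sirolimus: reduction to about one tenth of the dose, with monitoring.

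The contraindication is repeated for 3 of 4 groups. Sirolimus is the exception in both steps.

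**Step 3. Which rule catches sirolimus in the protocol?** The circular lists it among immunosuppressants metabolised by CYP3A4, so the general CYP3A4 paragraph in 7.1.1.5.2 applies. The named lists in that section do not include it.

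**Step 4. Safeguards outside Table 1.**

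| Safeguard | Where | Limit |
|---|---|---|
| Suspension given per local label | 4.2.2.3, 5.2, 5.2.2, flow chart note l, 7.1.5.2 | All 5 statements concern the suspension; none acts at entry or in the IV phase; the label conflicts on sirolimus |
| Investigator concern about safe participation | Exclusion 15 | Acts at entry, by judgement |
| Unnecessary-risk discontinuation | 5.8 | By judgement |
| Concomitant medication review, screening to end of treatment, and at eligibility confirmation | 6.0, 7.1.5.2 | Would find the drug, but gives no rule for it |

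None of these names sirolimus.

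**Step 5. Size of the interaction.** Circular Table 13 gives sirolimus ratios of 8.88 for AUC (90% CI 7.26 to 10.9) and 6.72 for Cmax (90% CI 5.62 to 8.03), with suspension 400 mg BID for 16 days. The Drug Interactions text places these results in healthy subjects. The trial's oral dose is 200 mg TID, so the size under this regimen is not known.

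**The case against.** The best reply is that the protocol is not silent. Exclusion 15 lets the investigator refuse any subject whose safe participation is in doubt, and it does not depend on Table 1. Section 5.8 requires withdrawal when a condition or circumstance creates unnecessary risk. Concomitant medication is reviewed repeatedly. Section 7.1.1.5.2 asks for caution, monitoring and dose adjustment, which is broadly what the circular's Drug Interactions text prescribes for sirolimus. For the suspension, the local label already applies, and its Contraindications section names the drug. The conflict lies inside the circular.

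Much of this stands. A reader might infer that nothing lies between a subject on sirolimus and the oral switch; the documents do not support that. But the entry and discontinuation safeguards rest on judgement, and the label wording leads to two instructions. The protocol turned the other three contraindicated groups into explicit bans and did not do so for the fourth.

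The count also has a limit. The QT and statin contraindications are class statements with named drugs, so 11 is a count of named drugs only. It says nothing about how completely Table 1 covers those classes.

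**Conclusion.** The omission is real and can be confirmed from the documents: 10 of 11 named drugs and 3 of 4 groups are banned, and sirolimus is left to a caution that permits what the suspension's label contraindicates. It is a point to consider, because existing safeguards reduce the risk and few subjects are likely to be affected. The small reach is an assumption: enrolment is limited to induction or first-relapse reinduction chemotherapy for AML and related MDS, and the documents give no frequency of sirolimus use. The PK estimate and sample size are not affected.

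Two stronger readings are tempting. A reader might infer that the combination is also contraindicated in the IV phase. The circular covers the suspension only, and neither the Investigator's Brochure nor the IV label is among these documents, so that is unknown. A reader might also infer that differences in posaconazole exposure between the IV and oral forms show which phase carries the larger interaction. Nothing in the documents ties posaconazole exposure to the size of the sirolimus effect. Circular Table 13 does not show steady scaling for other substrates either: the simvastatin AUC ratio is 10.31 at posaconazole 100 mg QD and 10.60 at 200 mg QD.

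**What to change.** 1. In section 5.2.2, state that the circular's contraindication governs for sirolimus, not its dose-reduction text, and that a subject taking sirolimus may not be switched to the oral suspension. These documents alone justify this.
2. Add sirolimus to Table 1, with a washout set by the sponsor, since the documents give none. Exclusions 13 and 14 and the 5.8 rule then apply without further edits. Apply the ban at entry and in the IV phase once the sponsor has checked it against the Investigator's Brochure and the IV label.

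The cost is one sentence, one table row and one sponsor check. The downside is that a rare subject is excluded, kept on IV if the check allows it, or moved to another drug.
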